Non-invasive Measurement of Blood Glucose,
Blood Pressure and Extrapolation of QRS
Complex Using a Wrist Wearable
Photoplethysmography Sensor

NCT05904769

10November2022

IRB Minimal Risk Protocol Template

Note: If this study establishes a human specimen repository (biobank) for research purposes, do not use this template. Use the Mayo Clinic Human Specimen Repository Protocol Template found on the IRB home page under Forms and Procedures at

[REDACTED]

First-time Use: Use this template to describe your study for a new IRB submission.

1. Complete the questions that apply to your study.
2. Save an electronic copy of this protocol for future revisions.
3. When completing your IRBe application, you will be asked to upload this document to the protocol section.

Modification: To modify this document after your study has been approved:

1. Open your study in IRBe. Click on the study 'Documents' tab and select the most recent version of the protocol. Save it to your files.
2. Open the saved document and activate "Track Changes".
3. Revise the protocol template to reflect the modification points, save the template to your files
4. Create an IRBe Modification for the study and upload the revised protocol template.

General Study Information

Principal Investigator: [name], MBBS, FACC, FHRSC

Study Title: Non-invasive measurement of blood glucose, blood pressure and extrapolation of QRS complex using a wrist wearable photoplethysmography sensor

Protocol version number and date: V1, November 10, 2022

Research Question and Aims

Hypothesis: A non-invasive wrist-based photoplethysmography (PPG) sensor may detect changes in blood glucose level and blood pressure. The PPG signal may also be used to extrapolate a waveform that may be used as a surrogate for the cardiac QRS complex.

Aims, purpose, or objectives:

1. Measure systolic and diastolic blood pressure detected by a wrist-based sensor and compare against standard of care noninvasive cuff blood pressure measurements and/or invasive arterial line measurements.
2. Extrapolate a surrogate waveform for the cardiac QRS complex by training and validating against the reference electrocardiograph (ECG) waveform.
3. Measure blood glucose levels detected by a wrist-based sensor and compare against fingerstick data obtained four times daily in hospitalized diabetic patients

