For blood pressure measurements, we will additionally study patients who undergo electrophysiologic procedures. We will compare readings on the wrist-based sensor to invasive arterial line measurements and/or noninvasive blood pressure readings obtained via a cuff-inflation in studies such as the tilt-table test. We typically monitor the electrocardiograph (ECG) waveform on these patients as well. During this study, we will collect continuous, time-synced PPG, blood pressure and ECG data from these patients for the duration of the procedure.

Subject Information

Target accrual is the proposed total number of subjects to be included in this study at Mayo Clinic. A "Subject" may include medical records, images, or specimens generated at Mayo Clinic and/or received from external sources.

Target accrual: 200 patients (100 patients hospitalized, and 100 patients undergoing EP procedures)

Subject population (children, adults, groups): adults

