**Inclusion Criteria:**

1. Diabetic patients on insulin undergoing four times daily blood sugar checks as part of standard of care.
2. Patients undergoing continuous monitoring for heart rate, ECG and blood pressure as part of their routine care.
3. Patients undergoing invasive and noninvasive electrophysiologic procedures.

Exclusion Criteria:

1. Patients unable to provide informed consent
2. Patients without arms as these are needed to wear the wrist-based sensor

Data Analysis

Power analyses may not be appropriate if this is a feasibility or pilot study, but end-point analysis plans are always appropriate even if only exploratory. Provide all information requested below or provide justification if not including all of the information.

Power Statement: This is a pilot study and thus is not specifically powered to reach a hard outcome. After this exploratory analysis, we will use this to appropriately power a larger study.

Data Analysis Plan: The data will be acquired with direct synchronization between glucose levels obtained by fingerstick or whole blood measurements and blood pressure (manually and invasive arterial line), ECG waveform and from the wrist-based PPG sensor. We will then compare the change in glucose level and blood pressure between measurements estimated by the sensor and by the standard glucose measurements. We will compare the changes in parameters between measurement time points using the standard measurements versus the wrist-based sensor using standard statistical methods (paired student t-test or Wilcoxon Signed Rank test). We will also evaluate what the absolute differences are between the 2 measurement approaches to determine the clinical significance. For the ECG comparison study, we plan to extrapolate a surrogate waveform from PPG and validate it against the reference QRS complex from the ECG waveform.

Endpoints**Primary:**

- 1) Difference between measurement of systolic and diastolic blood pressure using the wrist-based PPG sensor versus standard cuff-inflation and invasive measurement of blood pressure.
- 2) Difference between a surrogate waveform extrapolated from wrist-based PPG sensor versus standard QRS complex reported by the ECG sensor.
- 3) Difference between measurement of blood glucose level using the wrist-based PPG sensor versus standard blood-based measurement of blood glucose.

Secondary: N/A

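### Absolute differences and a test of mean change do not show whether the sensor tracks the individual; add a patient-mean benchmark and a within-patient analysis of changes

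*Combined protocol and SAP*

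**What the plan says.** The hypothesis, under Research Question and Aims, is that the wrist sensor "may detect changes in blood glucose level and blood pressure". Aim 3 sets the sensor against "fingerstick data obtained four times daily in hospitalized diabetic patients".

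The Data Analysis Plan gives two analyses for glucose and blood pressure:

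- **Changes.** "We will compare the changes in parameters between measurement time points using the standard measurements versus the wrist-based sensor", by a paired t-test or a Wilcoxon signed-rank test.
- **Absolute differences.** "We will also evaluate what the absolute differences are between the 2 measurement approaches to determine the clinical significance".

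The primary glucose and blood pressure endpoints are plain differences between sensor and reference. The documents give no acceptance limit, limits of agreement, error grid, benchmark predictor or measure of association between sensor change and reference change. They do not say whether the glucose or pressure output is calibrated to the individual; training is mentioned only for the ECG surrogate waveform (Aim 2). Target accrual is 100 hospitalized patients and 100 patients undergoing EP procedures.

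**The concern.** Each hospitalized patient contributes repeated readings that scatter around a personal level. The absolute difference between sensor and reference then depends on two things: how well the sensor follows the patient, and how much the patient varies in the first place. If the sensor starts from the right personal level, a patient who varies little yields small differences even when the optical signal adds nothing. The plan has no yardstick that separates the two.

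The analysis of change comes closer to the hypothesis. However, a paired t-test or signed-rank test asks whether the average (or typical) change is the same by both methods. It does not ask whether the sensor rises when that patient's glucose rises. Two methods can agree in mean change and be unrelated patient by patient.

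At stake is the interpretation of two of the three primary endpoints, and the planning figures for the larger study that this pilot is meant to inform.

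**Working it through.** The plan states no SD, accuracy limit, effect size or error rate, so it has no figure of its own to reproduce. Every SD below is an assumption.

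**1. Error of a sensor with no tracking.** Suppose the sensor returns the patient's true mean and readings vary normally around it with SD s. Then the mean absolute difference is s × √(2/π) = 0.80 s.

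| Measure | Assumed within-patient SD | Mean absolute difference |
|---|---|---|
| Glucose, mg/dL | 30 / 50 / 70 | 24 / 40 / 56 |
| Blood pressure, mmHg | 8 / 16 | 6.4 / 12.8 |

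**2. The same error can mean opposite things.** Compare this with a sensor that does track, with an assumed error SD of half the within-patient SD. Its mean absolute difference is 0.80 × s/2.

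- Glucose, s = 20 / 40 / 60 mg/dL: no tracking beyond the patient's mean and daily pattern gives 16 / 32 / 48; tracking gives 8 / 16 / 24.
- Systolic pressure, s = 6 / 8 / 10 / 15 mmHg: no tracking gives 4.8 / 6.4 / 8.0 / 12.0; tracking gives 2.4 / 3.2 / 4.0 / 6.0.

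An error of 16 mg/dL therefore comes from an uninformative sensor if s is 20 and from an informative one if s is 40.

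**3. What the planned test of change detects.** Simulation with 400 replicates, 100 patients and 12 readings each (four a day as in the plan; three days assumed). The test was applied to each patient's mean change at two-sided 0.05 (assumed; the plan states no level or unit of analysis). Assumptions:

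- Glucose: mean 170 mg/dL, between-patient SD 40, within-patient SD 20 to 60, time-of-day shifts −25/+5/+10/+10.
- Systolic pressure: mean 130 mmHg, between-patient SD 15, within-patient SD 6 to 15, shifts −2/0/+1/+1.

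| Sensor | Rejection, glucose | Rejection, systolic | Correlation of changes |
|---|---|---|---|
| Constant at patient's mean | 97–100% | 94% falling to 31–32% | 0 |
| Patient's mean plus time-of-day pattern | 3–7% | 4–6% | 0.08–0.61 |
| Tracking sensor | 3–5% | 4–8% | 0.90–0.93 |

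The mean of consecutive changes is (last − first)/11. The constant sensor is caught only because the assumed shifts build in a first-to-last difference of 10 − (−25) = 35 mg/dL, or 1 − (−2) = 3 mmHg. With no trend, rejection is about 5% by construction. The time-of-day sensor is rejected at about the nominal rate, as is the tracking sensor, so the test cannot tell them apart. The correlation of changes does.

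**4. A population average is a different case.** A time-of-day average that knows nothing about the patient had mean absolute differences of 36–57 mg/dL and 13–17 mmHg in the same simulation. It need not look accurate.

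**5. Choice of benchmark.** With independent readings, the mean of k earlier readings has mean absolute error 0.80 s × √(1 + 1/k): 1.13 s at k = 1, 0.89 s at k = 4, 0.83 s at k = 11. The previous value carried forward is the k = 1 case, so a sensor stuck at the patient's mean beats it with a ratio of 0.80/1.13 = 0.71. On continuous arterial data the reverse holds. With an assumed s of 12 mmHg and adjacent-reading correlation of 0.98, the SD of successive differences is 12 × √(2 × 0.02) = 2.4 and the carried-forward error is 0.80 × 2.4 = 1.9 mmHg. A sensor with a 3 mmHg error would then score 3/1.9 = 1.6. Constant bias distorts the ratio too: perfect tracking with a 45 mg/dL offset scores 45/32 = 1.4 against the patient-mean error at s = 40.

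**The case against.** Five points can be made for the plan.

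- **It does analyse change.** The comparison of changes stands next to the absolute differences and addresses the hypothesis. This stands in part: it is a real safeguard against a constant sensor when the reference has a trend. It does not cover a constant sensor without a trend, or a sensor that reproduces a daily pattern.
- **A sensor without signal cannot know the patient's usual value unless it is calibrated to the patient.** The documents describe no such calibration. This stands as a condition on the result.
- **The no-tracking errors are not obviously small.** A reader might infer that an uninformative sensor would look accurate. The documents do not support that: 24 to 56 mg/dL need not impress anyone, and a population average does worse. It could look accurate, most plausibly for blood pressure or stable glucose.
- **Half the accrual is EP patients** with continuous synchronized data. Clustering of values around a personal level is argued from ward readings and is not shown for procedural pressure. This stands, and is a reason to analyse the two groups separately.
- **It is a pilot:** "This is a pilot study and thus is not specifically powered to reach a hard outcome". That excuses the absence of a power calculation. It does not excuse primary endpoints that cannot be interpreted, and the protocol template itself asks for an endpoint analysis plan even in exploratory work.

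A reader might also infer that a larger study would be launched on a misleading error figure. The Power Statement says only that the results will be used to power one; no go/no-go rule depends on the absolute difference.

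**Conclusion.** The concern holds in a limited form. As written, neither the absolute differences nor the test of mean change can show that the sensor tracks an individual, so the plan does not test its own hypothesis for glucose or blood pressure.

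That a sensor with no tracking could look accurate depends on calibration to the individual, on within-patient variability that the documents do not give, and on roughly normal variation. The factor of 0.80 follows from the last of these; the mg/dL and mmHg figures are only as good as the assumed SDs. The rejection rates also depend on the assumed trends, length of stay and unit of analysis. That a test of mean change ignores individual agreement depends on none of these.

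This is a worthwhile, inexpensive improvement. It does not invalidate the study.

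**What to change.** Amend the Data Analysis Plan before analysis:

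1. **Benchmark error.** Beside the sensor's mean absolute error, report the error on the same paired readings of a benchmark equal to the mean of that patient's earlier reference values. Give the ratio with a patient-level bootstrap confidence interval, for glucose and for systolic and diastolic pressure. Use previous-value and time-of-day benchmarks only for intermittent ward readings, because carry-forward is nearly unbeatable on continuous data and check times have no meaning during EP procedures.
2. **Direct test of the hypothesis.** Report the within-patient association between sensor change and reference change, with a patient-level confidence interval, for ward and EP patients separately. For ward readings, set it beside the association that the time-of-day benchmark achieves, since a daily pattern alone reached 0.61 in one scenario. A pooled correlation of readings is no substitute: for a no-tracking patient-mean sensor it equals between-patient SD / √(between-patient SD² + within-patient SD²), which is 0.27 to 0.89 for between-patient SDs of 20 to 60 and within-patient SDs of 30 to 70 mg/dL.
3. **Bias.** Report mean bias separately. Do not make an error ratio below 1 the sole rule for claiming detection, because the ratio mixes bias with tracking and depends on which benchmark is chosen.

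The cost is a little more analysis on synchronized readings already planned, with no new patients or procedures. The headline accuracy may look less favourable.

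### Primary endpoint 2 has no QRS feature and no null comparator, so an average QRS placed at each detected pulse could score nearly as well as a true reconstruction

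*Combined protocol and SAP*

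**What the plan says.** The hypothesis, under Research Question and Aims, is that "The PPG signal may also be used to extrapolate a waveform that may be used as a surrogate for the cardiac QRS complex". Aim 2 is to "Extrapolate a surrogate waveform for the cardiac QRS complex by training and validating against the reference electrocardiograph (ECG) waveform".

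The second primary endpoint is the "Difference between a surrogate waveform extrapolated from wrist-based PPG sensor versus standard QRS complex reported by the ECG sensor".

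The Data Analysis Plan gives this endpoint one sentence: "For the ECG comparison study, we plan to extrapolate a surrogate waveform from PPG and validate it against the reference QRS complex from the ECG". The only named tests, "using standard statistical methods (paired student t-test or Wilcoxon Signed Rank test"), are attached to changes in parameters between measurement times. They are not clearly assigned to the ECG comparison.

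On data, Study Design and Methods says of the electrophysiology (EP) patients that "we will collect continuous, time-synced PPG, blood pressure and ECG data from these patients for the duration of the procedure".

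The documents give no similarity metric, alignment rule, QRS feature, separation of training from validation patients, comparator or acceptance threshold for this endpoint. The Power Statement says: "This is a pilot study and thus is not specifically powered to reach a hard outcome".

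**The concern.** The surrogate is produced by training on ECG. A model trained that way can learn the average QRS and place it wherever it detects a pulse. Comparing the result with the ECG as a waveform then mixes two questions: was the beat located, and was that beat's QRS recovered? The hypothesis is about the second. The Background argues for glucose and blood pressure, and gives no reason to expect the wrist signal to carry QRS duration or shape, so this cannot be taken for granted.

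If the two questions are not separated, a good waveform score could be read as a QRS surrogate when only a beat-timing detector has been shown. The pilot is meant to inform the powering of a larger study, which could then be built around a property never tested.

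**Working it through.** **Plan's own figure.** The only design number is accrual: "Target accrual: 200 patients (100 patients hospitalized, and 100 patients undergoing EP procedures"). 100 + 100 = 200 is consistent. It does not come from a power calculation, and no stated figure for endpoint 2 can be reproduced.

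**Inputs, all assumed.** Each QRS is a sum of Gaussian components stretched in proportion to its duration. Narrow beats are 90 ms (SD 4), wide beats 150 ms, noise is 2% of R amplitude, and sampling is at 250 Hz. The score is Pearson r between surrogate and ECG over all samples of all beats. Separate runs used somewhat different component shapes, so ranges are shown.

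**Step 1: fixed template, exact timing, same polarity.** The surrogate is one 90 ms QRS at every beat.

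| Wide beats | Pooled r |
|---|---|
| 2% | 0.990 |
| 5% | 0.983 to 0.984 |
| 10% | 0.974 to 0.976 |
| 20% | 0.957 to 0.964 |

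A further run put the 20% figure at about 0.95. On wide beats alone r is 0.87 to 0.90. The template's duration is constant, so it has no association with true duration and shows every wide beat as narrow.

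A simpler version gives each patient his or her own narrow template: mean r = (1 − f) × 1 + f × r_w, where f is the share of wide beats and r_w the template's correlation with a wide beat. With r_w about 0.834:
- f = 0.05: 0.95 + 0.0417 = 0.992
- f = 0.10: 0.90 + 0.0834 = 0.983
- f = 0.20: 0.80 + 0.1668 = 0.967

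**Step 2: unseen patients.** The template was averaged from 50 patients and scored in 50 others (narrow QRS 90 ms, SD 10; wide about 150 ms; 400 ms window). With exact alignment, median r is 0.988, 0.986 and 0.954 when 0%, 10% and 30% of patients have a wide QRS. Holding out patients therefore does not expose the template.

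**Step 3: timing error, 10% wide beats.** The fixed template is set against a surrogate that knows every beat's true duration, both with the same timing error.

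| Timing error SD | Fixed template | True duration known | Gap |
|---|---|---|---|
| 0 ms | 0.974 | 0.996 | 0.022 |
| 5 ms | 0.903 | 0.927 | 0.024 |
| 10 ms | 0.745 | 0.770 | 0.025 |
| 20 ms | 0.453 | 0.481 | 0.028 |

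A second run gave the template 0.89, 0.72, 0.41 and 0.19 at 5, 10, 20 and 40 ms. In the table, 10 ms of timing error costs 0.974 − 0.745 = 0.229, while losing all duration information costs 0.022. The score responds roughly ten times as strongly to the former (0.229 / 0.022 = 10.4).

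**Step 4: wide beats of opposite polarity, exact timing (an assumed extreme).** Template r is about 0.94, 0.86, 0.74 and 0.55 at 2%, 5%, 10% and 20% wide; another run gave 0.93 to 0.56. Gross reversal of shape does show in the score once such beats are common.

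**The case against.** The strongest reply is that the plan states no metric, so the correlation used above is the reviewer's choice, and the wording leaves room for a comparison of QRS features. That stands. A reader might infer that a fixed template would count as success, or that the endpoint is incapable of separating timing from shape. The documents support neither: there is no success criterion to meet, and a feature-based analysis is left unspecified, not excluded.

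Three further limits stand:
- High agreement is not assured. Placing a QRS from a wrist pulse requires correcting for the pulse delay, and the documents give no timing error. At 20 ms or more, r is below 0.5. This limits the size of the score but does not rescue the endpoint, because a surrogate with every duration right falls almost as far.
- A template placed at each pulse is not empty. It carries beat timing; what it lacks is beat-specific duration and shape.
- It is tempting to say that the EP cohort contains the wide, paced or ectopic beats that would expose a template. The documents describe no rhythms or QRS widths, and the cohort includes noninvasive procedures such as tilt-table testing.

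Pilot status and the hedged hypothesis also count against predicting that the trial will claim a QRS surrogate. They excuse the missing power calculation. They do not excuse an unspecified endpoint: the template's note under Data Analysis asks for endpoint analysis plans even in exploratory work.

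**Conclusion.** The concern holds in a limited form. As written, endpoint 2 gives no means of telling a reconstructed QRS from an average QRS placed at each pulse. Naming a pooled waveform metric such as correlation would not cure this, because in the illustration that score mainly tracks timing: at 10% wide beats, complete knowledge of duration adds only 0.02 to 0.03 at any timing error from 0 to 20 ms.

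The size rests wholly on assumed QRS shapes, wide-beat shares, timing errors and a chosen metric. It is strongest for duration and for wide beats shaped like the narrow ones, and weaker where abnormal beats are common and of opposite polarity. It does not show that a template would pass, or that the sensor carries nothing beyond timing. It is a change the sponsor should make before the endpoint is analysed.

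**What to change.** Using the time-synced recordings in the EP patients, split endpoint 2 into two parts:

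1. **Beat timing.** Report agreement in beat detection and timing between the sensor and the ECG.
2. **QRS content.** In patients not used for training, measure QRS duration on the surrogate and on the ECG for the same beats and report agreement. Where wide beats occur, show narrow and wide beats separately (for example, split at 120 ms), with the share of wide beats that the surrogate shows as wide.

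For part 2, use as comparator the average training-set QRS placed at each sensor-detected beat, under the same alignment rule as the surrogate. State the metric and alignment rule in advance. Describe the result as a QRS surrogate only if the extrapolated waveform beats that template; otherwise conclude on beat timing alone. The split point and the exact decision rule are one reasonable choice among several.

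The cost is some extra offline analysis of ECG already being collected, with no new data. The wide-beat group may be sparse, since the cohort's beat content is not documented, and the claim may shrink to beat timing.

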4. Measure blood glucose levels detected by a wrist-based sensor and compare against whole blood glucose identified in hospitalized patients undergoing anticipated blood glucose measurements

Background (Include relevant experience, gaps in current knowledge, preliminary data, etc.): Diabetics on insulin or several oral agents need to monitor blood sugar several times daily. However, checking blood sugar is invasive, requiring at minimum finger stick monitoring, and thus may be prone to issues with compliance. Recent data has suggested that spectral signatures that may be obtained using specific light frequencies over superficial vessels may allow for noninvasive measurement of blood glucose levels, including changes in levels over time. This may allow for non-invasive measurement of blood glucose that may permit pre-diabetic and diabetics to improve continuous and intermittent approaches to monitoring.

Additionally, we are at a paradigm shift in medicine where we are moving away from the traditional 6-monthly or annual follow-ups and entering an era of continuous monitoring. The novel wrist-based photoplethysmography (PPG) sensor would be able to measure systolic and diastolic blood pressure noninvasively and without the sensation of manual pressure. Thus, we can acquire many more data points on patients and potentially detect disease exacerbations before it is too late.

Study Design and Methods

Methods: *Describe in lay terms, completely detailing the research activities that will be conducted by Mayo Clinic staff under this protocol.*

Patients will be asked to wear a wrist-based PPG sensor (LifePlus, Inc) that will be worn throughout their hospitalization. They will be identified on the basis of being diabetic with anticipated four times daily blood glucose checks to be done as part of their regular inpatient care. Data collected will include patient demographics, body mass index, and Fitzpatrick skin tones. Timing of fingerstick checks as well as labs in which whole blood glucose measurements are obtained will be recorded and synchronized against evaluations recorded by the wrist-based sensor. These will then be compared offline for accuracy. Similar comparisons will be made for blood pressure readings and compared to standard vital sign checks on the floor.

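### Glucose agreement is summarised over all reference levels together, so a large error confined to low glucose could go unseen

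*Combined protocol and SAP*

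**What the plan says.** Under Endpoints, the third primary endpoint is the "Difference between measurement of blood glucose level using the wrist-based PPG sensor versus standard blood-based measurement of blood glucose". No summary statistic, glucose range or accuracy limit is attached to it.

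The Data Analysis Plan describes two further comparisons. Changes between time points are compared "using standard statistical methods (paired student t-test or Wilcoxon Signed Rank test"), and then: "We will also evaluate what the absolute differences are between the 2 measurement approaches to determine the clinical significance". Neither is split by reference glucose. The protocol does not mention low or high glucose, detection of lows, limits of agreement, or a minimum number of readings in any part of the range.

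Reference values come from care as usual. Inclusion criterion 1 is "Diabetic patients on insulin undergoing four times daily blood sugar checks as part of standard of care", and Methods identifies patients by "anticipated four times daily blood glucose checks to be done as part of their regular inpatient care", with laboratory glucose recorded as well. Aim 4 is worded somewhat more widely, covering hospitalised patients with anticipated glucose measurements. No quota or added sampling across the glucose range is described. Subject Information plans 100 hospitalised patients, and Methods has the sensor "worn throughout their hospitalization". The length of stay is not given.

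Background gives the intended use: "This may allow for non-invasive measurement of blood glucose that may permit pre-diabetic and diabetics to improve continuous and intermittent approaches to monitoring".

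**The concern.** A pooled average is weighted by where the readings happen to fall. In insulin-treated inpatients sampled on a routine schedule, most readings are likely to lie in the treated range and few below it. A sensor could follow glucose well where most readings lie, fail where few lie, and show pooled figures close to those of a sound sensor.

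Background proposes the sensor for glucose monitoring in diabetics and refers to those on insulin, for whom a missed low reading matters. The Power Statement says the pilot will be used to power a larger study. Pooled error figures carried forward would tell that study little about the low range.

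**Working it through.** The protocol states no SD, margin, alpha or expected error, so there is no planned figure to reproduce. Only the 100 hospitalised patients and four checks a day come from the documents. Everything else below is an assumption.

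**1. Dilution.** If an error b is confined to a share p of readings, the shift in the overall mean difference is p × b. With b = 40 mg/dL:
- p = 1%: 0.01 × 40 = 0.4 mg/dL
- p = 3%: 0.03 × 40 = 1.2 mg/dL
- p = 5%: 0.05 × 40 = 2.0 mg/dL

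**2. A worked scenario.** Assume 100 patients with 16 readings each (four days), patient means of 165 mg/dL (SD 30), within-patient SD 45 and sensor noise SD 15, all normal. The faulty sensor shows the larger of true glucose and 100 mg/dL, plus noise. The sound sensor shows true glucose plus the same noise.
- Total SD = √(30² + 45²) = √2925 = 54.1.
- Share below 70 = Φ((70 − 165)/54.1) = Φ(−1.757) = 0.0395, or about 63 of 1,600 readings. In simulation these fall in about 34 patients.
- Overall mean difference, faulty sensor = 54.1 × [φ(1.202) − 1.202 × Φ(−1.202)] = 54.1 × (0.1938 − 0.1379) = about +3.0 mg/dL.
- Mean reference value among lows = 165 − 54.1 × 0.0853/0.0395 = about 48, so the mean error below 70 is 100 − 48 = about +52 mg/dL.
- The untruncated normal puts about 26% of the lows under 40 mg/dL, which is unrealistic. Clipping reference values at 40 gives about +47, hence the range +47 to +52.
- Lows flagged by the faulty sensor = P(100 + 15Z < 70) = Φ(−2) = about 2%. The sound sensor flags about 82% (simulation).
- Mean absolute difference, sound sensor = 15 × √(2/π) = 12.0 mg/dL. For the faulty sensor it is about 14 (simulation: 13.9, or 13.7 with clipping at 40).

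**3. A different glucose model and fault.** Here glucose is lognormal with median 160 mg/dL, over 100 patients × 4 readings × 5 days, with noise SD 15. The sensor shows about 110 whenever the reference is below 70.

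| Share of lows | Overall mean difference | Mean absolute difference (sound: about 12) | Mean relative absolute difference (sound) | Error below 70 | Lows flagged (sound) |
|---|---|---|---|---|---|
| 1% | +0.5 | 12.3 | 8.6% (8.0%) | +47 | 0% (68%) |
| 3% | +1.5 | 13.1 | 10.2% (8.2%) | +50 | 0% (72%) |
| 5% | +2.6 | 14.0 | 12.4% (8.5%) | +52 | 0% (75%) |
| 10% | +5.7 | 16.5 | 19.0% (9.2%) | +57 | 0% (80%) |

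**4. Would a test show it?** In the model of step 3, a paired t-test on per-patient mean differences (two-sided 0.05) rejects in 23%, 89%, 100% and 100% of runs at the four shares. In the scenario of step 2 it rejects in essentially every run. It would be detecting a shift of a few mg/dL, with no indication of where in the range the error lies. If a sensor floored at 100 mg/dL is calibrated so that its mean error is zero, the test rejects in about 0-1% of runs while the sensor still misses 94-97% of lows.

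**5. How many lows to expect.** With 100 × 4 × days readings and shares of 1-5%, there would be 12-60 low readings for a 3-day stay, 20-100 for 5 days and 28-140 for 7 days.

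**The case against.** The strongest reply is that nothing here can pass. The study is an exploratory pilot with no accuracy limit or success criterion. A reader might infer that a sensor blind to lows would be reported as accurate, but the protocol has no rule that would produce that conclusion. This objection stands, and the point is limited to what the pooled results could be taken to support.

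The plan also does not confine itself to averages. In the worked scenario, without clipping, the SD of the differences is 18.8 against 15.0 mg/dL and the 99th percentile of the absolute difference is 65 against 38. An analyst who examined the spread, or tested levels, could notice a problem. That is fair, but the plan names its test for changes rather than levels and does not say which summary of the absolute differences will be given. None of these would locate the error at low glucose.

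The stored pairs could be banded later, and a low band may be too small for a precise estimate. Both are true. They favour a planned table with counts over an unplanned one.

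Several stronger readings do not hold:
- **High glucose also sparse.** Under the same assumptions the share above 180 mg/dL is 1 − Φ(15/54.1) = 39%, about 625 of 1,600 readings. Only lows are scarce.
- **The change comparison as evidence.** Its mean error is near zero for almost any sensor. In simulation it rejected in 0% of runs even for one showing a constant plus noise. That is a separate weakness, which bands do not address.
- **One absolute difference judged alike at every glucose level.** The plan is silent on this.
- **Blood pressure diluted to the same degree.** This was not shown. Methods describes continuous, synchronised recording during procedures, which is different sampling.

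**Conclusion.** The point holds in a limited form. Endpoint 3 and the Data Analysis Plan pool glucose agreement over all routine readings, and a large error confined to lows could be hidden in the pooled averages. At an assumed 1-5% share of lows, a 40 mg/dL error there moves the overall mean by 0.4-2.0 mg/dL. In the worked scenario the mean absolute difference rises only from about 12 to 14 mg/dL, while the error below 70 is about +47 to +52 mg/dL and detection of lows falls from about 82% to 2%.

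These sizes rest on assumed glucose distributions, sensor noise, stay lengths and fault types, none of which the documents give. The masking weakens as lows become more common: at a 10% share the relative error about doubles, although the plan does not specify relative error. The consequence is weak evidence about low glucose for the planned larger study. The documents do not show that a false accuracy claim will be made.

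**What to change.** In the Data Analysis Plan, with a reference from Endpoint 3, prespecify a table by reference glucose band, for example below 70, 70-180 and above 180 mg/dL. For each band give:
- the number of readings and the number of patients;
- the sensor-minus-reference difference and its spread;
- the absolute and relative absolute difference;
- for the low band, the share of reference lows that the sensor also places below 70.

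Use intervals that allow for repeated readings within patient. State that accuracy conclusions are limited to bands with adequate data and that the other bands are untested.

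The cost is a few lines of text and one table, with no extra sampling. The low band will be imprecise, possibly only a dozen readings if lows are 1% and stays are short, and the headline claim will be narrower. A matching table by reference systolic band for Endpoint 1 is optional.
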